6.2 Supplies and Accountability

The Investigator or designee will take inventory and acknowledge receipt of all shipments of Bellafill and microneedling dermarollers. Bellafill and dermarollers must be kept in a locked area with access restricted to designated study personnel. The Investigator or designee will also keep accurate records of the volumes of Bellafill injected and the number of dermarollers used. Unless other arrangements are confirmed in writing, unused syringes/dermarollers will be returned to the Sponsor.

6.3 Other Study Supplies

Supplies that are unique to this study will be provided by the Sponsor (e.g., UPTs, etc.). The Investigator is responsible for routine supplies related to pre and post-treatment care (e.g., alcohol wipes, gauze, etc.).

7. Study Methods and Procedures

7.1 Informed Consent and Subject Privacy

The purpose, procedures, risks, benefits, and alternatives to study participation will be discussed with each potential subject. Prior to any study-related procedures subjects must give their written informed consent. The subject must also give Authorization for Use and Release of Health and Research Study Information (HIPAA), authorization to take identifying clinical photographs for scientific use and other written documentation required by local regulations or the reviewing IRB prior to any study-related procedures.

7.2 Procedures for Final Study Entry

A subject is considered "Enrolled" when s/he has signed the IRB-approved informed consent form (ICF) and HIPAA authorization in the presence of the Investigator or designee. The Investigator (or designee) will collect and record medical and cosmetic procedure histories, and females of childbearing potential must have pregnancy test results evaluated as negative. All subjects must also have a negative Bellafill skin test. The Investigator will assure that each subject meets the washout requirements and eligibility criteria before randomization for study treatment.

7.3 Subject Identification and Numbering

All subjects who sign an ICF will receive a 3-digit subject number, starting at 001, and issued in ascending order. This subject number will be used to identify the subject throughout the study. Subjects withdrawn from the study will retain their subject number; new subjects will be allotted a new subject number.

7.4 Randomization and Blinding

All subjects attending Visit 4 (Week 12) will be randomized to receive "No Treatment" or "Bellafill". A computer-generated randomization schedule will link Randomization Numbers to specific treatment assignments at random on a balanced 1:1 basis. Site-specific Randomization Lists will be created for each site that contains unique and sequentially ascending Randomization Numbers. To randomize a subject and determine treatment allocation, the Investigator or delegate will refer to the lowest unused randomization number on the Randomization List.

The next eligible subject will receive the lowest available Randomization Number, allowing eligible subjects to be randomized to the study treatment sequence in

accordance with the randomization schedule. Randomization Numbers must not be omitted or reused.

This is an open-label study and blinding does not apply.

8. Efficacy Assessments

Prior to enrollment of any study subjects, the Investigators will be trained in the use of all efficacy assessment scales. Subjects will receive training on how to perform the self-assessments during the study. The following assessments will be conducted:

Acne Scar Assessment Scale (ASAS): a validated 5-point static scale assessing physician impression of acne scar severity;
Physician Global Aesthetic Improvement Scale (PGAIS): a 5-point dynamic scale assessing cosmetic improvement;
Subject Global Aesthetic Improvement Scale (SGAIS): a 5-point dynamic scale assessing cosmetic improvement;
Subject QOL Impact Scale: (33 questions): a 33-question survey that allows the subject to specifically address how acne scarring has affected his/her emotional and functional status.

See Appendix 1 for additional details regarding the assessments used in this study.

8.1 Photography

Facial photography will also be employed in this study. Baseline photographs will be used for PGAIS and SGAIS assessments. Canfield Scientific Inc. will provide each site with photographic equipment, training and an Instruction Manual prior to the start of the study.

9. Safety Assessments

Throughout the study, subjects will be instructed to report any unusual signs or symptoms to the Investigator.

The Investigator will solicit and record information about AEs, and concomitant medications, therapies and treatments. At each post-treatment visit, phone call, or email contact, the Investigator (or designee) will begin by asking the subject a general, non-directed question such as 'How have you been feeling since the last visit?' Directed questioning and examination will then be done as appropriate. All reported AEs will be documented in the eCRF.

10. Schedule of Study Activities

Subjects must have a negative Bellafill skin test prior to receiving study treatment. Additionally, a negative screening urine pregnancy test is required for women of childbearing potential. Please refer to the following assessment schedule for additional details:

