1.4 Current Clinical Study

A therapy that may stimulate collagen production, such as microneedling, is potentially a useful adjunct to atrophic acne scar treatment with Bellafill. The current pilot study will evaluate the effectiveness and safety of sequential treatment of microneedling followed by intra-scar injections with Bellafill.

2. Study Objective

To evaluate the effectiveness and safety of acne scar treatment that sequentially employs microneedling followed by Bellafill injections.

3. Study Design

[figure not shown]
This is an open-label, randomized, multicenter, prospective trial assessing the efficacy and safety of microneedling treatment alone vs. microneedling treatment followed by treatment with Bellafill for correction of distensible atrophic facial acne scars.

The study is divided into two study Periods. In **Period I**, subjects will attend a Screening visit (Week -4) and undergo the Bellafill skin test. At Visit 1 (Day 0), all subjects will commence microneedling treatment for their atrophic acne scars. Subjects will then return to the clinic at Week 3 and Week 6 (Visits 2 and 3, respectively) for follow-up evaluation and additional cycles of microneedling treatment.

At Week 12 (Visit 4), all subjects commence **Period II** and are randomized to Bellafill Treatment (Track A) or to No Treatment (Track B):

- Track A: Consists of three (3) study visits. At Visit 4, subjects randomized to the "Bellafill" group will receive treatment with Bellafill for their atrophic acne scars. Subjects return for Visit 5A (Month 1 after randomization) for evaluation and follow-up, and will receive touch-up injections with Bellafill to achieve optimal correction (if necessary). Subjects will then be followed-up at Visits 6A and 7A which will occur at Month 3 and Month 6, respectively, after their last Bellafill treatment.
- **Track B:** Consists of one (1) study visit. At Visit 4, subjects randomized to the "No Treatment" group will complete visit evaluations and then return for follow-up at Visit 5B (approx. Month 3 after randomization).

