10.2 Study Period I

10.2.1 Screening Visit (W -4)

The following activities will be conducted:

- Informed Consent/HIPAA
- Subject Demographics/Medical History and Inclusion/Exclusion Criteria
- UPT (if applicable)
- Concomitant Medication/Procedures
- Facial Scar Photography
- Bellafill skin test and record the location of placement for review at the next visit
 - If applicable, collect any AEs, if any observed immediately after skin testing.
- ASAS
 - Performed by the Investigator.
- AE Assessment

^{††} Visit to occur 24W after Visit 1 (i.e., approx. 3M after Visit 4)

¹ Assessments to be performed prior to study treatment (if applicable)

² If randomized to Bellafill treatment

³ Bellafill touch-up injections administered as necessary

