10.2.4 Visit 4 (W12 ± 1W)

The following activities will be conducted:

- Concomitant Medication/Procedures and AE assessment
- UPT (if applicable)
- PGAIS
 - The Investigator will refer to Baseline photographs for PGAIS evaluation.
- SGAIS
 - The subject will refer to Baseline photographs for SGAIS evaluation.
- Facial Scar Photography
- Randomization
 - Subject allocated to Track A (Bellafill Treatment) or Track B (No Treatment) as per Section 7.4.
- Bellafill injections Subjects randomized to Track A only
 - Document the number of scars treated as well as the method and volume of treatment.
- Scheduling of next clinic visit
 - Track A: Subjects randomized to Bellafill Treatment attend Visit 5a at 1 Month from this visit.
 - Track B: Subjects randomized to **No Treatment** attend Visit 5b at 24 Weeks from Visit 1 (i.e., approximately 3 Months from this Visit 4).

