10.3.3 Visit 7a (M6 ± 1W)

The following activities will be conducted 6M from Visit 4:

- Concomitant Medication/Procedures and AE assessment
- Facial Scar Photography
- ASAS and PGAIS
 - The Investigator will refer to Baseline photographs for PGAIS evaluation.
- QoL Scar Impact Scale and SGAIS
 - The subject will refer to Baseline photographs for SGAIS evaluation.
- Study Exit

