10.4 Study Period II (Track B – No Treatment)

10.4.1 Visit 5b (M3 ± 1W)

The following activities will be conducted 24W from Visit 1:

- Concomitant Medication/Procedures and AE assessment
- Facial Scar Photography
- ASAS and PGAIS
 - The Investigator will refer to Baseline photographs for PGAIS evaluation.
- QoL Scar Impact Scale and SGAIS
 - The subject will refer to Baseline photographs for SGAIS evaluation.
- Study Exit

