Appendix 1: Study Assessments

Appendix 2: Microneedling Procedure

Appendix 3: Skin Test Instructions for Use

Appendix 4: Bellafill Instructions for Use

APPENDIX 1: Study Assessments

A. Acne Scar Assessment Scale (ASAS): The ASAS is a static assessment scale that allows the Investigator to measure his/her impression of acne scar severity within the treatment area. The treatment area on each side of the face will be assessed separately, then will be averaged to obtain a global score.

Term	Grade	Description
Clear	1	No depressions are seen in the treatment area. Macular discoloration may be seen.
Very Mild	2	A single depression is easily noticeable with direct lighting (deep). Most or all of the depressions seen are only readily apparent with tangential lighting (shallow).
Mild	3	A few to several, but less than half of all the depressions are easily noticeable with direct lighting (deep). Most of the depressions seen are only readily apparent with tangential lighting (shallow).
Moderate	4	More than half of the depressions are apparent with direct lighting (deep).
Severe	5	All or almost all the lesions can be seen with direct lighting (deep).

B. Physician Global Aesthetic Improvement Scale (PGAIS): The Investigator will refer to baseline photographs and assess global overall improvement (but without considering untreated scars) as per the following:

Rating	Description
5 = Much improved	Marked improvement in appearance from the initial condition, touch-up treatment(s) is not indicted
4 = Improved	Obvious improvement in appearance from the initial condition, but a touch-up or re-treatment is indicated
3 = No change	The appearance is essentially the same as the original condition
2 = Worse	The appearance is worse than the original condition
1 = Much Worse	The appearance is much worse than the original condition

C. Subject Global Aesthetic Improvement Scale (SGAIS): The degree of aesthetic improvement will be assessed by the subject using the SGAIS as defined below. The subject will refer to baseline photographs and assess global overall improvement (but without considering untreated scars) as per the following:

Rating	Description
5 = Much improved	Marked improvement in appearance from the initial condition
4 = Improved	Obvious improvement in appearance from the initial condition
3 = No change	The appearance is essentially the same as the original condition
2 = Worse	The appearance is worse than the original condition

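### Period II PGAIS and SGAIS are rated only against pre-microneedling photographs, which can attenuate and add noise to the Track A v Track B contrast; the pre-Bellafill Visit 4 photographs and ratings have no stated use

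*Combined protocol and SAP*

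**What the plan says.** Section 8.1 gives a single reference for both global scales: "Baseline photographs will be used for PGAIS and SGAIS assessments". The visit sections repeat it. Section 10.4.1 (Visit 5b) reads "The Investigator will refer to Baseline photographs for PGAIS evaluation", and Section 10.3.3 (Visit 7a) reads "The subject will refer to Baseline photographs for SGAIS evaluation". Sections 10.2.4 (Visit 4) and 10.3.2 (Visit 6a) follow the same rule. The term Baseline photographs is not defined. The schedule in Section 10.1 places photography at Screening, Visit 4, Visit 7a and Visit 5b, so the Screening set is the only one that precedes microneedling. Appendix 1 also anchors both scales to the subject's initial or original condition.

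Section 3 says that at Day 0 "all subjects will commence microneedling treatment for their atrophic acne scars", with further cycles at Weeks 3 and 6 and randomisation at Week 12. Section 10.2.4 lists "Facial Scar Photography" at Visit 4. Footnote 1 of the schedule puts the Visit 4 photographs, PGAIS and SGAIS before any study treatment given at that visit. No rating is said to use the Visit 4 photographs, and Section 12.2 does not say whether the Visit 4 ratings enter the comparison.

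In Appendix 1, grade 3 is no change on both scales. For PGAIS, grade 4 is "Obvious improvement in appearance from the initial condition, but a touch-up or re-treatment is indicated" and grade 5 is "Marked improvement in appearance from the initial condition, touch-up treatment(s) is not indicted". SGAIS has the same two improvement grades without the touch-up wording.

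**The concern.** Section 3 sets microneedling alone against microneedling followed by Bellafill. Everyone has finished microneedling when the tracks separate, so the randomised contrast is the change after Visit 4. A rating against the Screening face mixes that change with the change before Visit 4. This has two consequences.

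- **Ceiling.** A subject at grade 4 at Visit 4 has one grade left, and a subject at grade 5 has none.
- **Noise.** Differences between subjects in microneedling response enter every Period II rating in both tracks.

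The other scales do not fill the gap. ASAS is static and needs no photograph, but it is not scheduled at Visit 4. The QoL scale is completed at Visit 1 and then only at exit. PGAIS and SGAIS are therefore the only efficacy scales with a value just before Bellafill, and the plan neither uses that value nor re-references the later ratings. With about 45 subjects, a real added effect could be missed.

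**Working it through.** **The plan's figure.** Section 12.1 gives approximately 45 subjects as the Sponsor's opinion, with no effect size, SD, rate or power, so there is nothing to reproduce. At 1:1 (Section 7.4), 45 gives 22 v 23 if everyone reaches Visit 4. Alpha is 0.05 (Section 12.2); two-sided is assumed.

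**Full five-grade scale.** All parameters below are assumptions.

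- Period I gain M ~ Normal(m, SD s), in grades.
- Period II change P ~ Normal(0, 0.8) in both tracks, plus 0.8 in Track A.
- Rating noise has SD 0.5, and cut-points lie at -1.5, -0.5, 0.5 and 1.5.
- The Visit 4 rating is M + noise graded; the Screening-referenced rating is M + P + noise graded; the Visit 4-referenced rating is P + noise graded.
- Tests are Mann-Whitney, and for the adjusted analysis a linear model with track and Visit 4 rating. There are 12,000 simulated trials per row, with a Monte Carlo standard error of at most 0.5 point.

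| s | m | at grade 5 at Visit 4 | power, Screening reference | same, adjusted for Visit 4 rating | power, Visit 4 reference |
|---|---|---|---|---|---|
| 1.0 | 0 | 9% | 43.5% | 61.4% | 73.5% |
| 1.0 | 0.5 | 19% | 42.5% | 59.0% | 73.5% |
| 1.0 | 1.0 | 33% | 39.0% | 53.1% | 73.5% |
| 1.0 | 1.5 | 50% | 35.6% | 45.7% | 73.6% |
| 0.3 | 0 | 0.5% | 69.6% | 71.3% | 73.6% |
| 0.3 | 0.5 | 4% | 68.0% | 69.1% | 73.2% |
| 0.3 | 1.0 | 20% | 64.4% | 65.3% | 73.6% |
| 0.3 | 1.5 | 50% | 55.5% | 56.1% | 73.4% |

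**Separating the two mechanisms.**

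- Neither strong (s = 0.3, m = 0): 73.6 - 69.6 = 4.0 points lost.
- Mostly variation (s = 1, m = 0): 73.5 - 43.5 = 30.0 points.
- Mostly ceiling (s = 0.3, m = 1.5): 73.4 - 55.5 = 17.9 points.
- Both (s = 1, m = 1.5): 73.6 - 35.6 = 38.0 points.

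With no Bellafill effect (s = 1, m = 0.5 to 1.5; 2,000 trials each), all three analyses reject in 4-5% of trials.

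**If Bellafill adds less where Period I gain was larger** (slope -0.5, s = 1, m = 0.5 to 1.5; 2,000 trials each), power is 54-55% with the Screening reference, 69-72% when adjusted, and 68% with the Visit 4 reference. Here adjustment does at least as well as re-referencing.

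**Share rated 4 or 5.** Appendix 4 gives SGAIS improvement of 67/87 = 77.0% for Bellafill and 19/46 = 41.3% for saline. These are borrowed for illustration only. Let q be the share already improved by microneedling, independent of Period II response. Against Screening photographs each rate p becomes 1 - (1 - q)(1 - p), so the difference is (1 - q) × 35.7 points.

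| q | Track A | Track B | difference (points) | exact Fisher power, 22 v 23 |
|---|---|---|---|---|
| 0 | 77.0% | 41.3% | 35.7 | 64% |
| 20% | 81.6% | 53.0% | 28.6 | 46% |
| 40% | 86.2% | 64.8% | 21.4 | 31% |
| 60% | 90.8% | 76.5% | 14.3 | 18% |
| 80% | 95.4% | 88.3% | 7.1 | 5% |

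**The case against.** The tempting stronger reading is that microneedling uses up both improvement grades and hides the Bellafill effect. The documents do not support it. They give no Period I response rate or SD, and a subject at grade 3 or 4 at Visit 4 can still rise. For PGAIS, grade 5 also depends on no touch-up being indicated, so a subject whose scars still merit treatment after microneedling belongs at grade 4 and can move to 5. SGAIS has no such anchor.

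A reader might also infer that the comparison is biased. Both tracks share the reference, so it remains valid under the null; what suffers is sensitivity.

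Further points stand:

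- The Screening reference fits the objective in Section 2, which concerns the whole sequence.
- A pre-Bellafill PGAIS and SGAIS already exist for adjustment.
- The study is a pilot with exploratory inference and no named primary scale.
- If Period I response varies little, the loss is modest: about 5-9 points for mean gains of 0.5-1.0 at SD 0.3.
- The dichotomised illustration merges grades 4 and 5, which the plan does not require.

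These points limit the size of the problem but do not remove it. Section 12.2 plans between-group tests at 0.05 and does not mention adjustment. Under an independent Bellafill effect with SD 1, adjustment recovers only part of the loss (from 35.6% to 45.7% when half of subjects are already at grade 5).

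**Conclusion.** The point holds as a loss of sensitivity that is cheap to reduce. Every Period II PGAIS and SGAIS rating is tied to the pre-microneedling face, while the randomised question starts at Visit 4. Under the assumed 0.8-grade effect, power is 73-74% with the Visit 4 reference and roughly 35-70% with the Screening reference, for Period I mean gains of 0 to 1.5 grades and SDs of 0.3 to 1. Variation between subjects in Period I response drives the loss as well as the ceiling. All of these parameters are assumptions, and the documents cannot narrow the range. Neither bias under the null nor a complete masking of Bellafill's effect is shown.

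**What to change.** 1. In Section 8.1, define Baseline photographs as the Screening photographs. Keep the rating against them to describe the whole sequence.
2. In Section 12.2, prespecify that the Track A v Track B comparison of Screening-referenced PGAIS and SGAIS adjusts for the same scale's Visit 4 rating. This needs no new data.
3. In Sections 10.3.2, 10.3.3 and 10.4.1 and Appendix 1 B and C, add a second PGAIS and SGAIS rating against the Visit 4 photographs at Visits 6a, 7a and 5b. Report it for the between-track comparison alongside item 2.
4. Reconcile the Section 10.1 schedule, which has SGAIS at Visit 6a, with Section 10.3.2, which omits it.

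The cost is one more rating per scale, rater and visit; the reference photographs are already scheduled. There are two downsides to name. The second rating adds comparisons to a plan with no multiplicity adjustment. It also asks open-label raters about the interval in which the tracks differ, so expectation can influence it, although the existing rating is open to the same influence.

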10.1 Assessment Schedule

								Pe	riod II	
Period I			Track A Bellafill			Track B No-Tx				
	Visit	Screening	1	2	3	4	5a	6a	7a	5b
	1 week = 7D 1 month = 28D	W -4	D0	W3 ±3D	W6 ±3D	W12 ±1W	M1 ±1W	M3 [†] ±1W	M6 [†] ±1W	M3 ^{††} ±1W
Inf	ormed Consent	Х								
Inc	l/Excl Criteria, Med Hx	Х	X confirm							
UF	PT (if applicable)	Х	X ¹			X ¹	X ¹			
Fa	cial Scar Photography	Х				X ¹			Х	Х
Ве	llafill Skin Test	X Placement	X Reading							
Microneedling Treatment			Х	Χ	Х					
Ra	ndomization					R				
Bellafill Injections Initial injection Touch-up						l²	T ³			
ş	ASAS (Investigator)	Х						Χ	Х	Χ
nen	PGAIS (Investigator)					X ¹		Х	Х	Х
PGAIS (Investigator) SGAIS (subject) QoL Scar Impact Scale						X ¹		Χ	X	Χ
Ass	QoL Scar Impact Scale (subject)		X ¹						Х	Х
Со	n Meds/Procedures	X	Χ	Χ	Χ	Х	Χ	Χ	Х	Χ
Ad	verse Events	Х	Х	Χ	Χ	Χ	Χ	Χ	Χ	Х

[†] Visits to occur 3M and 6M after last injection of Bellafill (i.e., initial treatment or touch-up treatment)

10.2 Study Period I

10.2.1 Screening Visit (W -4)

The following activities will be conducted:

- Informed Consent/HIPAA
- Subject Demographics/Medical History and Inclusion/Exclusion Criteria
- UPT (if applicable)
- Concomitant Medication/Procedures
- Facial Scar Photography
- Bellafill skin test and record the location of placement for review at the next visit
 - If applicable, collect any AEs, if any observed immediately after skin testing.
- ASAS
 - Performed by the Investigator.
- AE Assessment

^{††} Visit to occur 24W after Visit 1 (i.e., approx. 3M after Visit 4)

¹ Assessments to be performed prior to study treatment (if applicable)

² If randomized to Bellafill treatment

³ Bellafill touch-up injections administered as necessary

10.2.2 Visit 1: Treatment Visit (D0)

The following activities will be conducted:

- Inclusion/Exclusion Criteria (confirmation)
- UPT (if applicable)
- Review skin test results and inclusion/exclusion criteria to confirm eligibility
- QoL Scar Impact Scale
 - Performed by the subject prior to receiving microneedling treatment.
- Microneedling treatment (see Section 5.1)
- Concomitant Medication/Procedures and AE assessment
- Provide HSV Prophylaxis with Acyclovir for subjects with a medical history of cold sores (may be provided prior to Visit 1 at the discretion of the Investigator).

10.2.3 Visit 2 and Visit 3 (W3 ± 3D and W6 ± 3D)

The following activities will be conducted:

- Microneedling treatment (see Section 5.1)
- Concomitant Medication/Procedures and AE assessment
- Provide HSV Prophylaxis with Acyclovir for subjects with a medical history of cold sores.

10.2.4 Visit 4 (W12 ± 1W)

The following activities will be conducted:

- Concomitant Medication/Procedures and AE assessment
- UPT (if applicable)
- PGAIS
 - The Investigator will refer to Baseline photographs for PGAIS evaluation.
- SGAIS
 - The subject will refer to Baseline photographs for SGAIS evaluation.
- Facial Scar Photography
- Randomization
 - Subject allocated to Track A (Bellafill Treatment) or Track B (No Treatment) as per Section 7.4.
- Bellafill injections Subjects randomized to Track A only
 - Document the number of scars treated as well as the method and volume of treatment.
- Scheduling of next clinic visit
 - Track A: Subjects randomized to Bellafill Treatment attend Visit 5a at 1 Month from this visit.
 - Track B: Subjects randomized to **No Treatment** attend Visit 5b at 24 Weeks from Visit 1 (i.e., approximately 3 Months from this Visit 4).

